10.2 Laboratory Data

Laboratory data (Hematocrit (%), Total Cholesterol (mmol/L), LDL (mmol/L), HDL (mmol/L), Triglycerides (mmol/L), Hemoglobin (g/L), ALT (U/L), AST (U/L)) at Visit 1, Visit 4, Visit 5

and Early Terminations will be summarized and presented descriptively for the ALL and TID treatment groups.

Laboratory data change from baseline (Visit 1) results at Visit 4, Visit 5 and Early Terminations will be summarized and presented descriptively for the ALL and TID treatment groups. Change from baseline results will be analysed using a two-sided paired t-test or a non-parametric equivalent if warranted by the data.

Laboratory data (Hematocrit (%), Total Cholesterol (mmol/L), LDL (mmol/L), HDL (mmol/L), Triglycerides (mmol/L), Hemoglobin (g/L), ALT (U/L), AST (U/L)) at Visit 1, Visit 4 and Early Terminations will be summarized and presented descriptively for the BID treatment group.

Laboratory data change from baseline (Visit 1) results at Visit 4 and Early Terminations will be summarized and presented descriptively for the BID treatment group. Change from baseline results will be analysed using a two-sided paired t-test or a non-parametric equivalent if warranted by the data.

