2.0 STUDY OBJECTIVES

2.1 Primary Objective

The primary objective of the study is to measure patient satisfaction with testosterone replacement therapy before (for non-naïve patients), during and after treatment with Natesto™.

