5.2 Secondary Efficacy Endpoints

The secondary efficacy endpoints are:

- change in satisfaction for each TSQM domain from Visit 2 (Day 30) to Visit 4 (Day 90) for naïve BID patients
- change in satisfaction for each TSQM domain from Visit 2 (Day 30) to Visit 5 (Day 120) for naïve TID patients
- change in total qADAM score from Visit 1 (Day 0) to Visit 4 (Day 90) for non-naïve BID patients
- change in total qADAM score from Visit 1 (Day 0) to Visit 5 (Day 120) for non-naïve TID patients
- change in total qADAM score from Visit 1 (Day 0) to Visit 4 (Day 90) for naïve BID patients
- change in total qADAM score from Visit 1 (Day 0) to Visit 5 (Day 120) for naïve TID patients
- change in total qADAM score from Visit 1 (Day 0) to Visit 5 (Day 120) for non-naïve ALL patients
- change in total qADAM score from Visit 1 (Day 0) to Visit 5 (Day 120) for naïve ALL patients
- change in total qADAM score from Visit 1 (Day 0) to Visit 5 (Day 120) for non-naïve and naïve ALL patients

- patient preference of therapy as measured by Part A of the Treatment Preference and Use Questionnaire at Visit 1 (Day 0) for the following groups of patients:
 - non-naïve and naïve ALL
 - non-naïve ALL
 - naïve ALL
 - non-naïve BID
 - naïve BID
 - non-naïve TID
 - naïve TID
- patient preference of therapy as measured by Part B of the Treatment Preference and Use Questionnaire for the following groups of non-naïve patients:
 - BID at Visit 4 (Day 90)
 - TID at Visit 4 (Day 90)
 - TID at Visit 5 (Day 120)
- patient preference of therapy as measured by Part C of the Treatment Preference and Use Questionnaire for the following groups of naïve patients:
 - BID at Visit 4 (Day 90)
 - TID at Visit 4 (Day 90)
 - TID at Visit 5 (Day 120)
- Natesto™ dosing frequency by hypogonadism treatment status (naïve/non-naïve) assigned at Visit 4 (Day 90)

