7.0 DATA CONVENTIONS

7.1 Definitions

Visit 1 (Day 0) is defined as the day in which the patient provides informed consent and starts the study. All study days are determined relative to Visit 1 (Day 0).

End of treatment is defined as the day on which the last dose of treatment is taken. This date was not collected for this study.

End of study is defined as the last day on which data were collected from the patient. Using the Early Termination Visit eCRF, it is the date of early termination. Using the Visit 6 - Post Study Follow-Up (Day 150) eCRF, it is the post study follow-up date. Otherwise, it is the date of last contact, if the patient was lost to follow-up, or the date of death, if the patient died.

Baseline serum testosterone values will be defined as those values recorded on Visit 1 (Day 0). Naive patients were asked for 2 measurements (average used in analysis) and non-naive patients were asked for 1 measurement at Baseline (Visit 1/Day 0).

Serum Testosterone will be reported in (nmol/L). If value is reported in (ng/dL) then value will be multiplied by 0.0347 to convert to (nmol/L).

Testosterone collected in (pmol/L) will be considered Free Testosterone and will not be used in any analyses.

Hematocrit will be reported in (%). Values will be multiplied by 1 and if the value is less than 1 then the value will be multiplied by 100.

Total Cholesterol will be reported in (mmol/L). If value is reported in (mg/dL) then value will be divided by 38.67 to convert to (mmol/L).

LDL will be reported in (mmol/L). If value is reported in (mg/dL) then value will be divided by 38.67 to convert to (mmol/L).

HDL will be reported in (mmol/L). If value is reported in (mg/dL) then value will be divided by 38.67 to convert to (mmol/L).

Triglycerides will be reported in (mmol/L). If value is reported in (mg/dL) then value will be divided by 88.57 to convert to (mmol/L).

Hemoglobin will be reported in (g/L). If value is reported in (g/dL) then value will be divided by 0.1 to convert to (g/L).

ALT and AST will be reported in (U/L).

Study duration (days) will be defined as the (end of study date – date of informed consent + 1).

The ALL treatment group will be defined as patients who were either naïve or non-naïve.

The BID treatment group will be defined as patients who were either naïve or non-naïve and did not titrate to TID (Visit 5/Day 120).

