10.3 Testosterone Data

Testosterone data (nmol/L) at Visit 1, Visit 4, Visit 5 and Early Terminations will be summarized and presented descriptively for the non-naïve TID, naïve TID, non-naïve ALL, naïve ALL and the non-naïve and naïve combined ALL treatment groups.

Testosterone data change from baseline (Visit 1) results at Visit 4, Visit 5 and Early Terminations will be summarized and presented descriptively for the non-naïve TID, naïve TID, non-naïve ALL, naïve ALL and the non-naïve and naïve combined ALL treatment groups. Change from baseline results will be analysed using a two-sided paired t-test or a non-parametric equivalent if warranted by the data.

Testosterone data (nmol/L) at Visit 1, Visit 4, Visit 5 and Early Terminations will be summarized and presented descriptively for the non-naïve BID and naïve BID treatment groups.

Testosterone data change from baseline (Visit 1) results at Visit 4, Visit 5 and Early Terminations will be summarized and presented descriptively for the non-naïve BID and naïve BID treatment groups. Change from baseline results will be analysed using a two-sided paired t-test or a non-parametric equivalent if warranted by the data.

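### Section 10.2 reports and tests laboratory change from Day 0 only for naïve and non-naïve patients together, which mixes starting testosterone with what appears to be switching

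*SAP*

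**What the plan says.** Section 10.2 covers hematocrit, hemoglobin, total cholesterol, LDL, HDL, triglycerides, ALT and AST. For ALL and TID, "Laboratory data change from baseline (Visit 1) results at Visit 4, Visit 5 and Early Terminations will be summarized and presented descriptively", followed by a two-sided paired t-test or non-parametric equivalent. For BID, "Laboratory data change from baseline (Visit 1) results at Visit 4 and Early Terminations will be summarized and presented descriptively for the BID treatment group", with the same test.

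Section 7.1 fixes what the groups contain. "The ALL treatment group will be defined as patients who were either naïve or non-naïve". BID and TID are defined in the same way, with titration status added. Section 10.2 names no other group.

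On what Day 0 means, the primary objective in section 2.1 measures satisfaction "before (for non-naïve patients), during and after treatment with Natesto™". Secondary objective 2 (section 2.2) sets preference against prior testosterone therapy. In the section 3.0 schedule, Day 0 is the start of treatment, and only non-naïve patients complete the TSQM on that day.

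Testosterone is handled differently. Section 10.3 reports change for the "non-naïve TID, naïve TID, non-naïve ALL, naïve ALL and the non-naïve and naïve combined ALL treatment groups", and for non-naïve BID and naïve BID separately.

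**The concern.** A change from baseline is only as clear as the baseline. For a naïve patient, Day 0 is a value before testosterone, so the later change reflects starting treatment. For a patient who was on another testosterone product until Day 0, the change reflects moving between products. These answer different safety questions, and there is no reason to expect the same size or even the same sign for hematocrit, hemoglobin or lipids.

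Averaging them gives a number that depends on how many of each kind were enrolled. Safety monitoring is secondary objective 4, and the section 10.2 tests are the only planned inference on these laboratory values. A small, non-significant pooled change could be reported as little laboratory effect when naïve patients had moved appreciably. Knowing the enrolled mix would not repair this: one pooled mean cannot be solved for two cohort means.

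**Working it through.** The plan states no effect size, SD, power or naïve share for laboratory values, so there is no figure to reproduce. The check is first textual, then an illustration on assumed inputs.

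**1. Is any laboratory change split by cohort?** The groups in section 10.2 are ALL, BID and TID. By section 7.1 each holds naïve and non-naïve patients. Nothing in section 10.2 is split.

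**2. Does the plan separate the cohorts elsewhere?**
- Testosterone change (10.3): split in BID, TID and ALL, plus one combined ALL row.
- qADAM change (5.2, 9.2): seven endpoints, of which six are split (two cohorts × BID, TID, ALL) and one is combined.
- TSQM change (5.1, 5.2): split, with Visit 1 as baseline for non-naïve patients and Visit 2 for naïve patients.
- Demographics, disease characteristics, medical history, study duration and concomitant medication (11.1 to 11.5): shown overall and by cohort.

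Section 10.2 is thus out of line with the plan's own practice for change from baseline in testosterone, qADAM and TSQM.

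**3. Size of the dilution.** Let p be the naïve share, and let d₁ and d₀ be the mean changes in naïve and non-naïve patients, in units of the within-cohort SD of change.

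- Pooled mean = p·d₁ + (1 − p)·d₀
- Pooled SD = √[1 + p(1 − p)(d₁ − d₀)²]

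From the SAP: about 100 patients (4.0) and two-sided 0.05 (8.0). Assumed: p = 30%, 50% and 70%; d₁ = +0.5; d₀ = 0, −0.25 or −0.5; all 100 patients with a value at the visit.

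Example, p = 30%, d₀ = 0: mean = 0.3 × 0.5 = 0.15; SD = √(1 + 0.21 × 0.25) = 1.026; mean/SE = 0.15 × √100 / 1.026 = 1.46; power by normal approximation = 0.31. In the naïve patients alone (n = 30), 0.5 × √30 = 2.74 and power = 0.78.

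| Assumed non-naïve change | Quantity | p = 30% | p = 50% | p = 70% |
|---|---|---|---|---|
| 0 | pooled mean | +0.15 | +0.25 | +0.35 |
| 0 | pooled power | 0.31 | 0.68 | 0.93 |
| −0.25 | pooled mean | −0.03 | +0.13 | +0.28 |
| −0.25 | pooled power | 0.06 | 0.22 | 0.74 |
| −0.5 | pooled mean | −0.20 | 0.00 | +0.20 |
| −0.5 | pooled power | 0.44 | 0.05 | 0.44 |
| any | power, naïve patients alone | 0.78 | 0.94 | 0.99 |

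Dilution needs no opposing movement: with non-naïve patients flat, the naïve change simply shrinks by the factor p. Full cancellation needs a particular combination, here equal cohorts with equal and opposite changes. In every scenario shown, the naïve subgroup has more power to detect its own change than the pooled test, despite its smaller size.

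**The case against.** **Day 0 exposure is inferred.** The SAP does not define non-naïve or say whether earlier therapy was still running at Day 0. Rating a past product on the TSQM does not prove current exposure, and a schedule that starts at Day 0 would not show an earlier washout. This stands as a limit. Against it, section 7.1 puts consent and study start on one day and the schedule starts treatment on that day, which leaves no interval for an on-study washout. If non-naïve patients had been off therapy for long enough, the baselines would be less unlike and the point weaker.

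**The figures are invented.** They are assumptions, and the plan offers nothing better. They show direction and mechanism only.

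**The data may be visible elsewhere.** Section 8.0 leaves layout to the Table Mock-Up, which is not at hand, and promises listings for what that document omits. A listing is neither a summary nor a test, and section 10.2 commits to no cohort row.

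**The p-values are exploratory.** Section 8.0 says so and leaves them unadjusted, so no formal decision turns on the pooled test. That lowers the stakes but does not make the pooled estimate easier to interpret.

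**A stronger reading is tempting:** that qADAM and testosterone share the fault, because section 5.2 lists "change in total qADAM score from Visit 1 (Day 0) to Visit 5 (Day 120) for non-naïve and naïve ALL patients" and section 10.3 has a combined ALL row. The SAP does not support it. Both measures are also summarised and tested by cohort, so a pooled result driven by one cohort would be visible beside it. Nor does the SAP support reading symptom improvement from naïve patients alone: objective 1 is not so limited, and three non-naïve qADAM change endpoints are listed.

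**Conclusion.** The point holds for section 10.2. That laboratory change is pooled in every planned group and split in none follows directly from sections 7.1 and 10.2. That the pooled change mixes starting with switching is a reasonable inference from sections 2.1, 2.2 and 3.0, conditional on no effective washout before Day 0.

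The size cannot be known from the SAP. Under the stated assumptions the pooled change keeps between 30% and 70% of the naïve change when non-naïve patients stay flat. Cancellation is possible, but nothing in the SAP shows that it is likely.

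This is a modest gap in exploratory safety tables, worth closing because it costs little. It does not extend to the split testosterone and qADAM analyses, whose only shortcoming is an unlabelled combined row.

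**What to change.** - In section 10.2, present laboratory values and change from baseline separately for naïve and non-naïve patients within ALL, BID and TID, and apply the paired test by cohort, following section 10.3. Where TID cells are small, keep those rows descriptive.
- Keep the combined rows if wanted, labelled as mixed-baseline. Describe the naïve row as change after starting therapy and the non-naïve row as change after switching. With no control arm, neither should be called a drug effect.
- State in section 7.1 what the non-naïve Day 0 value represents, including whether any break in therapy preceded it, with a reference to the protocol.
- Add the same mixed-baseline label to the combined ALL rows for qADAM and testosterone. No other change is needed there.

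The cohort flag and all values are already collected, so the change is confined to SAP wording and table shells. The price is smaller groups and wider intervals per cohort, chiefly in TID, and more unadjusted exploratory p-values.

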10.3 Testosterone Data

Testosterone data (nmol/L) at Visit 1, Visit 4, Visit 5 and Early Terminations will be summarized and presented descriptively for the non-naïve TID, naïve TID, non-naïve ALL, naïve ALL and the non-naïve and naïve combined ALL treatment groups.

Testosterone data change from baseline (Visit 1) results at Visit 4, Visit 5 and Early Terminations will be summarized and presented descriptively for the non-naïve TID, naïve TID, non-naïve ALL, naïve ALL and the non-naïve and naïve combined ALL treatment groups. Change from baseline results will be analysed using a two-sided paired t-test or a non-parametric equivalent if warranted by the data.

Testosterone data (nmol/L) at Visit 1, Visit 4, Visit 5 and Early Terminations will be summarized and presented descriptively for the non-naïve BID and naïve BID treatment groups.

Testosterone data change from baseline (Visit 1) results at Visit 4, Visit 5 and Early Terminations will be summarized and presented descriptively for the non-naïve BID and naïve BID treatment groups. Change from baseline results will be analysed using a two-sided paired t-test or a non-parametric equivalent if warranted by the data.

10.4 Vital Signs

Vital signs (Systolic Blood Pressure (mmHg), Diastolic Blood Pressure (mmHg), Heart Rate (beats/minute), Oral/Tympanic Temperature (Celcius), BMI (kg/m²)) at Visit 1, Visit 4 and Early Terminations will be summarized and presented descriptively for the BID treatment group.

Vital signs (Systolic Blood Pressure (mmHg), Diastolic Blood Pressure (mmHg), Heart Rate (beats/minute), Oral/Tympanic Temperature (Celcius), BMI (kg/m²)) at Visit 1, Visit 4, Visit 5

and Early Terminations will be summarized and presented descriptively for the ALL and TID treatment groups.

10.5 Physical Examination

Physical examination (General Appearance, Skin, Nose, Head/Neck, Heart, Lungs, Abdomen, Neuromuscular, Extremities, Other) at Visit 1, Visit 4, Visit 5 and Early Terminations will be summarized and presented categorically for the ALL treatment group.

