3.0 STUDY OVERVIEW

This is a phase 4, multi-centre study consisting of two study periods and a post study follow-up.

90-Day Treatment Period: With potential extension by 30 days for those patients requiring a dose increase, as determined by the treating physician. Participants receiving 122.5mg of Natesto™ (5.5 mg of testosterone) per nostril twice daily may have an increased daily dose adjustment on Day 90, based on their hypogonadism symptoms.

1-Day Study Completion Period: Patient will return to the site for examination, discussion of symptoms with physician and questionnaire completion. Serum testosterone levels will be determined for all patients on Day 90 (BID dose) and on Day 120 for the TID patients.

Post Study Follow-Up: All study patients will be followed up at Day 150 after the Treatment Phase to determine if they have continued using NATESTO and why (or why not?).

Schedule of Procedures

Study Phase	Treatment Period						
	Treatment Start	Efficacy Analysis				Post Study Follow Up	Early Withdrawal/Termination
	Day 0	Day 30 +/- 3 days	Day 60 +/- 3 days	End of Study: BID Patients Day 90 +/- 3 days	End of Study: TID Patients Day 120 +/- 3 days	Day 150 +/- 3 days	
Visit	1	2	3	4 ^a	5 ^b	6	
Location/Type	clinic	telephone	telephone	clinic	clinic	telephone	clinic
Study Procedures:							
Inclusion/exclusion criteria	X						
Informed consent	X						
Medical history	X			X	X		
Demographics	X						
Physical examination + nasal exam	X			X	X		X
Height and weight	X			X	X		X
Vital signs (HR, BP, RR, and temperature)	X			X	X		X
Serum total testosterone plus safety labs	X ^c			X	X ^d		X
Participant training on NATESTO administration	X						
Provide Study Drug Access Card for NATESTO	X						
Provide Pharmacy Prescription	X			X ^g			
Potential study drug daily dose increase to TID				X			
TSQM	X ^e	X	X	X	X		X
qADAM	X ^f	X	X	X	X		X
Patient Preference + Use	X			X	X		X
Concomitant medications	X	X	X	X	X		X
Assess adverse events	X	X	X	X	X		X
Assess voluntary treatment continuation						X	

- a. All patients are required to complete Visit 4
- b. Only patients assigned to NATESTO TID are required to complete Visit 5
- c. Naïve patients will require confirmation of hypogonadism by serum testosterone within the last 6 months
- d. Only patients who continued on TID
- e. TSQM to be completed by non-naïve patients only
- f. qADAM to be completed by all patients

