8.0 ANALYSIS STRATEGY

A Table Mock-Up (TMU) document which will illustrate the details of presentation and analysis for data collected in this study will accompany this document. A brief discussion of the presentation, planned inferences, and statistical methods follows below. Data not presented in the TMU document will be provided in listings.

Continuous variables will be summarized descriptively by number of observations, number of missing observations, mean, standard deviation, median, 1st quartile, 3rd quartile, minimum and maximum. Categorical variables will be summarized descriptively as frequency counts and percentages.

A number of p-values may be presented in the reported tables for exploratory purposes. Statistical testing will be performed at the two-sided 0.05 significance level unless otherwise specified in the sections that follow. These p-values will not be adjusted for multiple comparisons.

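### The planned tables show nasal and other examination findings only as by-visit counts for pooled patients, and vital signs without change from Visit 1, so new findings within patients are not shown

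*SAP*

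**What the plan says.** **Physical examination.** The schedule in SAP Section 3.0 lists "Physical examination + nasal exam" at Day 0, Day 90, Day 120 and Early Termination, and Section 5.3 makes physical examination a safety endpoint. Section 10.5 names ten categories, Nose among them. Findings at Visits 1, 4 and 5 and at Early Termination "will be summarized and presented categorically for the ALL treatment group"; no other group is named. Section 8.0 defines a categorical summary as frequency counts and percentages.

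**Vital signs.** Section 10.4 plans by-visit summaries for each dosing group. For BID, data "at Visit 1, Visit 4 and Early Terminations will be summarized and presented descriptively for the BID treatment group". The other two groups have Visit 5 as well: data at that visit "and Early Terminations will be summarized and presented descriptively for the ALL and TID treatment groups". In Section 8.0, a descriptive summary covers the number of observations, the number missing, and "mean, standard deviation, median, 1st quartile, 3rd quartile, minimum and maximum". Section 10.4 mentions no change from Visit 1.

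**Other safety domains.** Section 10.2 does plan a change, for example for BID: "Laboratory data change from baseline (Visit 1) results at Visit 4 and Early Terminations will be summarized". Section 10.3 does the same for testosterone. Section 10.1 tabulates adverse events for ALL, BID and TID.

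**The concern.** The study drug is given per nostril, so the nasal examination is the part of the physical examination most directly tied to the product. The natural safety question is how many patients with a normal nose at Visit 1 had an abnormal one later. By-visit counts in a pooled group do not answer it, for two reasons. New and resolved findings cancel in the counts, and the patients in each column are not the same. The data needed to answer the question are collected at the scheduled visits but would not be summarized that way.

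The vital signs gap is smaller. Blood pressure, heart rate and BMI are measured at the same clinic visits as the laboratory tests, yet only the laboratory and testosterone data have a planned within-patient change. The SAP gives no reason for the difference.

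**Working it through.** The SAP gives no figure on this point, so there is none to reproduce. The check has four steps.

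**1. What by-visit counts can identify.** Take *n* patients examined at both visits, *a* abnormal at Visit 1 and *b* abnormal at Visit 4. The number newly abnormal lies between max(0, *b* − *a*) and min(*b*, *n* − *a*). The sample size of about 100 is from Section 4.0. The abnormal counts are assumed.

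| *n* | *a* (Visit 1) | *b* (Visit 4) | Lower bound | Upper bound | Newly abnormal |
|---|---|---|---|---|---|
| 100 | 15 | 15 | max(0, 0) = 0 | min(15, 85) = 15 | 0 to 15 |
| 100 | 10 | 5 | max(0, −5) = 0 | min(5, 90) = 5 | 0 to 5 |
| 100 | 10 | 10 | max(0, 0) = 0 | min(10, 90) = 10 | 0 to 10 |
| 100 | 10 | 15 | max(0, 5) = 5 | min(15, 90) = 15 | 5 to 15 |

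Even with the same patients at both visits, the counts leave a wide range. A two-by-two table of Visit 1 status against later status gives the number directly.

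**2. Who is in each column of the ALL table.** From the schedule and its footnotes in Section 3.0:

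- Visit 1: all patients.
- Visit 4: all patients still in the study.
- Visit 5: required only of patients assigned to TID.
- Early Termination: only patients who leave.

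Let *P1* be the proportion abnormal among all patients at Visit 1. Let *T1* and *T5* be the proportions among the titrated patients at Visits 1 and 5. If all titrated patients attend Visit 5, the visible difference between the columns is

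*T5* − *P1* = (*T5* − *T1*) + (*T1* − *P1*).

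The first term is change within the titrated patients. The second is only the difference between those patients and everyone else at the start. The planned table does not show *T1*, so the two cannot be separated. The same holds for Early Termination.

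**3. When TID exposure begins.** Section 3.0 places the dose increase, and the new prescription, at Visit 4. A patient later classed as TID therefore reaches the Visit 4 examination on BID. Visit 5 is the scheduled examination that follows TID dosing.

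**4. Safety domains side by side.**

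| Domain (SAP section) | By visit | Split by BID and TID | Change from Visit 1 |
|---|---|---|---|
| Adverse events (10.1) | not applicable | yes | not applicable |
| Laboratory data (10.2) | yes | yes | yes |
| Testosterone (10.3) | yes | yes | yes |
| Vital signs (10.4) | yes | yes | **no** |
| Physical examination (10.5) | yes | **no** | **no** |

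For vital signs, two visit means give the mean change only if the same patients contribute to both. The spread of individual changes also depends on the correlation *r* between visits: variance of change = *s1*² + *s4*² − 2·*r*·*s1*·*s4*. The planned table does not give *r*.

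**The case against.** The case on the other side has five parts.

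- **Other outputs cover part of the gap.** Section 10.1 counts patients with adverse events by preferred term for ALL, BID and TID, so a new nasal abnormality reported as an adverse event would appear there by dosing group. Section 8.0 sends data not in the mock-up tables to listings. This stands in part. It is why one should not infer that the trial is unable to report new nasal findings. However, the SAP does not say that a new examination finding is recorded as an adverse event, and a listing is not a planned summary.
- **The table mock-up document may add a shift table.** Section 8.0 calls its own text brief and leaves presentation details to that document, which is not at hand. This is possible, but Section 10.5 specifies neither a shift nor a split.
- **A BID and TID split adds little before Visit 5.** This stands. A reader might infer from the missing split that TID nasal exposure is hidden at every visit. The timeline does not support that: at Visit 4, a split would sort patients by a later decision. The ALL column at Visit 5 is already, in effect, the status of TID patients. What is missing is those patients' own Visit 1 and Visit 4 status beside it.
- **Vital signs are well described already.** This also stands. A reader might take them to be shown only as means, or not by dosing group. Sections 8.0 and 10.4 rule out both readings. Within the TID group, patients must have reached Visit 4 to be titrated, so changing membership between Visits 1 and 4 matters little there.
- **The magnitude is assumed.** True. The example shows only what by-visit counts leave open, not what happened in this trial.

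**Conclusion.** The point holds as a gap in safety presentation. Section 10.5 plans no within-patient comparison with Visit 1 for any part of the examination, and its visit columns are not like for like. The planned table therefore does not show how many patients developed a nasal abnormality on treatment. Section 10.4 plans no change from Visit 1 for vital signs, out of line with Sections 10.2 and 10.3.

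The size cannot be taken from the SAP. In the assumed example with 15 abnormal at each visit among the same 100 patients, the table would leave 0 to 15 new abnormalities possible. The conclusion rests on reading Section 10.5 with the definition of categorical summaries in Section 8.0, and on the mock-up document adding no shift table.

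It is a modest improvement and not an error that threatens the trial. Nothing in Sections 10.4 or 10.5 contradicts the safety endpoints in Section 5.3, and the efficacy analyses are unaffected.

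**What to change.** In SAP Section 10.5, keep the by-visit counts, which give prevalence at each visit, and add within-patient shift tables (normal or abnormal), at least for Nose:

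- from Visit 1 to Visit 4, and from Visit 1 to Early Termination, for ALL;
- from Visit 1 to Visit 5, and from Visit 4 to Visit 5, for the TID group.

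Add a footnote that a TID-group patient's Visit 4 examination reflects BID exposure, because titration takes place at that visit.

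In SAP Section 10.4, add a descriptive paired change from Visit 1 for blood pressure, heart rate and BMI, in the groups and at the visits already listed. No test is needed.

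The cost is a few lines of SAP text, the matching table shells and a few more tables, all from data already collected. TID cells may be small, so those shifts should be read as counts of patients.
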